## 9. PHARMACOKINETIC ANALYSES

### 9.1. Primary Pharmacokinetic Analyses

There are no primary Pharmacokinetic analyses, only secondary. The primary objective is Pharmacodynamic, the average systolic blood pressure (SBP) over 6-hr post-dosing after 8 weeks, this is described in Section 11.

### 9.2. Secondary Pharmacokinetic Analyses

#### 9.2.1. Endpoint / Variables

 
To characterize the pharmacokinetics of daprodustat
 
	
 
Plasma concentrations of daprodustat and metabolites and derived pharmacokinetic parameters including maximum observed concentration (Cmax), time of occurrence of Cmax (tmax), terminal phase half-life (t1/2), area under concentration-time curve from time zero to 24 hours (AUC[0-24]), and area under concentration-time curve from time zero to infinity (AUC[0-inf]) as appropriate
 

---	---

#### 9.2.1.1. Drug Concentration Measures

Refer to [Appendix 5: Data Display Standards & Handling Conventions \(Standards for Pharmacokinetic\)](#)

#### 9.2.1.2. Derived Pharmacokinetic Parameters

Pharmacokinetic parameters will be calculated by standard non-compartmental analysis according to current working practices and using the currently supported version of WinNonlin. All calculations of non-compartmental parameters will be based on actual sampling times. Pharmacokinetic parameters listed will be determined from the plasma concentration-time data, as data permits.

Blood samples for pharmacokinetic (PK) analysis of daprodustat and its metabolites (GSK2391220 [M2], GSK2531403 [M3], GSK2487818 [M4], GSK2506102 [M5], GSK2531398 [M6], and GSK2531401 [M13]) will be collected at the time points indicated in Section 14.2.1, Time and Events Table. The actual date and time of each blood sample collection will be recorded. The timing of PK samples may be altered and/or PK samples may be obtained at additional time points to ensure thorough PK monitoring. Details of PK blood sample collection (including volume to be collected), processing, storage and shipping procedures are provided in the SRM. If the participant is unable to provide a sufficient blood quantity per time point or there is significant concern for this by the participant or investigator, these serial blood draws may be omitted.

Plasma analysis will be performed under the control of Bioanalysis, Immunogenicity, and Biomarkers - In Vitro/In Vivo Translation Platform/Scinovo, GlaxoSmithKline, the details of which will be included in the SRM. Concentrations of daprodustat and its metabolites (GSK2391220 [M2], GSK2531403 [M3], GSK2487818 [M4], GSK2506102

[M5], GSK2531398 [M6], and GSK2531401 [M13]) will be determined in plasma samples using the currently approved bioanalytical methodology. Raw data will be archived at the bioanalytical site (detailed in the SRM).

### 9.2.2. Summary Measure

All pharmacokinetic endpoints will be summarized in tabular form. Descriptive statistics (n, arithmetic mean, standard deviation, minimum, median, maximum) will be calculated for all pharmacokinetic endpoints by regimen. In addition, for AUC(0-24, AUC(0-inf),  $C_{max}$ ,  $t_{1/2}$ , geometric means and geometric CVs (CVb(%)) will be calculated for each regimen. Geometric mean and geometric CV% will not be calculated for  $t_{max}$ .

A participant listing of individual PK parameters for each treatment group will be provided. Pharmacokinetic parameters will be summarized by treatment group using descriptive statistics.

### 9.2.3. Population of Interest

The secondary pharmacokinetic analyses will be based on the PK population, unless otherwise specified.

### 9.2.4. Strategy for Intercurrent (Post-Randomization) Events

Not required.

### 9.2.5. Statistical Analyses / Methods

Details of the planned displays are provided in [Appendix 12: List of Data Displays](#) and will be based on GSK Data Standards and statistical principles.

Unless otherwise specified, endpoints / variables defined in Section 9.2.1 will be summarised using descriptive statistics, graphically presented (where appropriate) and listed.

Geometric mean= $\exp$  (mean on  $\log_e$  scale)

CVb (%)= $\text{SQRT}(\exp(\text{SD}^2)-1) \times 100$ , where SD is the standard deviation of the  $\log_e$ -transformed data.

## **10. POPULATION PHARMACOKINETIC (POPPK) ANALYSES**

### **10.1. Statistical Analyses / Methods**

POPPK is not evaluated for this study. The primary objective is Pharmacodynamic, the average systolic blood pressure (SBP) over 6-hr post-dosing after 8 weeks, this is described in Section [11](#).

## 11. PHARMACODYNAMIC AND BIOMARKER ANALYSES

### 11.1. Primary Pharmacodynamic Analyses

#### 11.1.1. Endpoint / Variables

Primary Objectives	Primary Endpoints

 
To compare the effect of daprodustat to epoetin alfa on blood pressure (BP) after Acute Challenge 2 (8 weeks of hemoglobin [Hgb) maintenance therapy)
 
	
 
Average of systolic blood pressure (SBP) as measured by ambulatory blood pressure monitoring (ABPM) over 6-hr post-dosing after 8 weeks of Hgb maintenance therapy
 

The primary endpoint is average systolic blood pressure (SBP) over 6-hr post-dosing after 8 weeks. Other variables used in the primary endpoint model include: treatment, prior ESA dose (low/high), post-HD/pre-Acute Challenge 1 SBP, difference between post-HD/pre-Acute Challenge 2 SBP and post-HD/pre-Acute Challenge 1 SBP, and treatment by (difference in post-HD SBP between Acute Challenge 1 and 2) interaction.

#### 11.1.2. Summary Measure

Average of systolic blood pressure (SBP) as measured by ambulatory blood pressure monitoring (ABPM) over 6-hr post-dosing after 8 weeks (i.e. Day 57) of Hgb maintenance therapy.

#### 11.1.3. Population of Interest

The primary pharmacodynamics analyses will be based on the Intent-To-Treat population, unless otherwise specified.

If there are protocol deviations that are thought to potentially impact the primary endpoints (defined as at least 10% of the ITT population being excluded from the PP population), an exploratory sensitivity analysis may be considered using the PP population.

Any such important protocol deviations will be identified before DBR and the subsequent sensitivity analysis on the PP population will be documented in the CSR.

#### 11.1.4. Strategy for Intercurrent (Post-Randomization) Events

ABPM data is collected every 15 minutes for the first 6-hrs and then every 20 minutes thereafter until 24-hrs post dose. In order to reduce the extent of missing ABPM data due to device issues, the device is designed to retry measuring blood pressure if it fails to record a BP during the scheduled timepoint. In addition, after both Acute Challenge 1 and 2, the 24-hr ABPM results will be checked for data quality as defined in the Project Requirement Specification (PRS). If the ABPM fails the QC criteria following Acute Challenge 2, one additional Acute Challenge may be made in a subsequent, mid-week dialysis visit 1 week later if the participant agrees. This repeat Acute Challenge 2 would replace the failed QC Acute Challenge 2.

For these participants who have a failed QC of the ABPM for a given acute challenge day, the data that is available from the ABPM device will be used during a sensitivity analysis on the primary endpoint. For those participants that fail QC both Acute Challenge 2, and a repeat Acute Challenge 2, the repeat Acute Challenge 2 data will be utilized.

Since participants who discontinue randomized study medication are withdrawn from the study and would have already performed their Day 1 acute challenge, multiple imputation will be used to attempt to impute what the missing data would have been had the participant not stopped randomized study medication. These participants who are early withdrawn will have their missing Day 57 ABPM data imputed to be included in a sensitivity analysis on the primary endpoint. This sensitivity analysis will include those participants who both early withdrawal and have their ABPM data imputed as well as those participants whose ABPM data did not pass QC for a given day. Details of the multiple imputation can be found in Section 14.6.6.

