9.3. Data Analysis Considerations

9.3.1. Analysis Populations

The primary population of interest is the intent to treat (ITT) population defined as all randomized subjects that received at least one dose of study treatment.

In addition, a per-protocol population may be investigated. Details will be provided in the Reporting and Analysis Plan (RAP) for the study.

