**14.6.6. Pharmacodynamic and Biomarker**

Pharmacodynamic and Biomarker
ABPM Data

 
• Only subjects whose ABPM data QC passes will be included in the PD TLFs
 
• ABPM data will be recorded during the challenge agents on Day 1, Day 57, and repeat Day 57 if applicable.
 
• The pre-acute challenge measurement will come from ABPM data if the first included ABPM measurement is within <math>\pm 10</math> min of the adjusted start time of the ABPM device. 
 
○ Else, the pre-acute challenge measurement will be taken from the vitals dataset, post-dialysis measurement only. This is for Day 1, Day 57, repeat Day 57. If day 1 is missing from the vitals dataset, then week-2 or screening can be used. 
 
▪ The time used for replacing excluded ABPM measurement with a vitals measurement will remain the adjusted start time of the ABPM device.
 
 
 
 
 

CONFIDENTIAL

205665

Pharmacodynamic and Biomarker					

 
If there is an additional ABPM data for Day 57, this means the subjects original Day 57 ABPM data failed QC and this data will not be included for any analysis
 
6, 8, 12, and 24-hour averages will be calculated using the following method: 
 
Each hour will be averaged (up to 4 measurements per hour for the first 6 hours)
 
Then average the 6, 8, 12, and 24 hour measurements
 
This applies for ABPM data (SBP, DP, MAP, HR)
 
Missing or data that has been deemed not of good quality based on QC criteria, will be flagged with an excluded flag. These data will not be used when averaging ABPM.
 
This will be calculated for 6, 8, 12 and 24 hours
 
Example:
 
 
 
					
Hour	ABPM				Average
	1 st Measurement	2 nd Measurement	3 rd Measurement	4 th Measurement	
0-1	***, not used for average ABPM, being used as baseline BP value unless baseline comes from vitals	112	116	115	= (112+116+115)/3 = 114.33
1-2	120	118	121	X, missing	= (120+118+121)/3 = 119.67
2-3	120	118	121	125	= (120+118+121 + 125)/4 = 121
3-4	120	118	121	125	121
4-5	120	118	121	125	121
5-6	120	118	121	125	121
6 Hour Average					(114.33 +119.67+121+121 +121+121)/6 = 119.67

 
X represents missing data
 
					

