## CONFIDENTIAL

205665

Pharmacodynamic and Biomarker: Tables					
No.	Population	IDSL / Example Shell	Title	Programming Notes	Deliverable
4.37.	ITT	PDT8	Summary of Analysis of Average 6hr ABPM SBP post-AC2, Imputed Data	Use imputed missing values for AC2 for early withdrawal subjects, calculate 6hr averages for those subjects who failed QC for any AC.  For subjects who AC2 failed QC, 6hr average SBP will be calculated without imputation	DR, SAC
4.38.	ITT	PDT3	Summary of Analysis of Average 8hr ABPM SBP post-AC2		DR, SAC
4.39.	ITT	PDT3	Summary of Analysis of Average 12hr ABPM SBP post-AC2		DR, SAC
4.40.	ITT	PDT3	Summary of Analysis of Average 24hr ABPM SBP post-AC2		DR, SAC
4.41.	ITT	PDT4	Summary of Analysis of AUEC SBP over 24hr post-AC2, Imputed Data	
 
If more than 25% of subjects are excluded from the ABPM AUEC analysis then this sensitivity analysis will be performed for the AC2 SBP AUEC model               
 
If during dry-run less than 25% of subjects are excluded, then table is not needed for dry-run
 
 
 
	SAC
Additional PD tables					
4.42.	ITT	PDT10	Summary of Subjects who QC Pass Acute Challenges	Column by treatment, row by Day 1 and Day 57, where Day 57 includes repeat AC2	SAC

CONFIDENTIAL

205665

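### The primary analysis is labelled ITT but is limited to subjects who pass a QC of the 24-hour ABPM recording; a 0-6 h evaluability rule would fit the 6-hour endpoint better

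*SAP*

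**What the plan says.** **Population.** Protocol 9.3.1 takes the primary population to be ITT, "defined as all randomized subjects that received at least one dose of study treatment". SAP 4 repeats this, and SAP 11.1.3 states: "The primary pharmacodynamics analyses will be based on the Intent-To-Treat population, unless otherwise specified". Table 4.5, the primary result (SAP 14.12.8), is listed as ITT.

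**Restriction.** SAP 14.6.6, under ABPM Data: "Only subjects whose ABPM data QC passes will be included in the PD TLFs".

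**What QC judges.** Protocol 4.1 and 7.5.1 and SAP 11.1.4 all apply the check to the whole recording: "the 24-hr ABPM results will be checked for data quality as defined in the Project Requirement Specification (PRS"). The criteria appear in neither document.

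**What happens after a failure.** One further Acute Challenge 2 (AC2) may be done a week later if the subject agrees. SAP 11.1.4: "This repeat Acute Challenge 2 would replace the failed QC Acute Challenge 2". For recordings that fail, "the data that is available from the ABPM device will be used during a sensitivity analysis on the primary endpoint". The programming note to Table 4.37 adds: "For subjects who AC2 failed QC, 6hr average SBP will be calculated without imputation". Protocol 9.2.1 recruits until 25 per arm are projected to complete and pass QC for AC2, and SAP 14.7.1 replaces subjects who do not pass.

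**Endpoint.** Average SBP over the first 6 hours after dosing at AC2 (Protocol 9, SAP 11.1.2).

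**The concern.** The gate and the endpoint cover different periods. A pass or fail given to 24 hours of readings decides whether a 6-hour average enters the primary analysis. A subject can be randomised, dosed, complete AC2 and have a computable primary outcome, yet appear only in a sensitivity analysis. The note to Table 4.37 shows that the SAP expects failed AC2 recordings to yield a 6-hour average.

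The restriction seems to reach Day 1 as well. SAP 11.1.4 speaks of failure on a given challenge day, and the multiple-imputation text in SAP 14.6.6 lists Day 1 failures among the subjects that the sensitivity analysis adds. They are therefore outside the primary analysis.

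At stake are post-randomisation exclusions that the endpoint does not require, a label that does not describe the analysed set, and some recruitment effort.

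**Working it through.** **1. The plan's own figures.** Inputs from Protocol 9.2.1: SD 16 mmHg, difference 15 mmHg, 5% significance level (taken as two-sided, to match the two-sided 95% CI in Protocol 9.4.1), 25 per arm at AC2. Two-sample t-test:

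- standard error = 16 × √(2/25) = 4.53 mmHg
- half-width of the 95% CI = 2.011 × 4.53 = 9.10 mmHg (stated 9.1)
- noncentrality = 15 / 4.53 = 3.31, power = 90.1% (stated as above 90%, and 90% in Table 6)

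With 31 per arm the same method gives 8.13 mmHg and 95.3% (stated 8.1 and 95%). The design figures reproduce.

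**2. Where the readings fall.** Schedule from Protocol 7.5.1 and SAP 11.1.4: every 15 minutes to hour 6, then every 20 minutes to hour 24.

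- hours 0-6: 6 × 4 = 24 readings (the first serves as baseline in SAP 14.6.6)
- hours 6-24: 18 × 3 = 54 readings
- share after the primary window: 54 / 78 = 69%

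**3. Could later hours alone fail a recording?** The criteria are unseen, so this is an illustration only. Assume that QC is a single threshold on the percentage of valid readings out of 78, and that all 24 early readings are valid.

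| Assumed threshold | Valid readings needed | Fails if later valid readings (of 54) are below |
|---|---|---|
| 60% | 47 | 23 |
| 70% | 55 | 31 |
| 75% | 59 | 35 |
| 80% | 63 | 39 |

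Under such a rule a recording complete for the primary endpoint can fail. Under a rule that judges 0-6 h separately it cannot.

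**4. Cost of AC2 failures when they are replaced.** Let f be the assumed failure rate after any repeat. Completers needed per arm = 25 / (1 − f). Randomised per arm, with the plan's 20% withdrawal, = 25 / (0.8 × (1 − f)).

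| f (assumed) | Completers per arm | Extra | Randomised per arm | Share of randomised analysed |
|---|---|---|---|---|
| 0% | 25 | 0 | 31.25 → 32 | 78% |
| 5% | 26.3 → 27 | 2 | 32.9 → 33 | 76% |
| 10% | 27.8 → 28 | 3 | 34.7 → 35 | 71% |
| 15% | 29.4 → 30 | 5 | 36.8 → 37 | 68% |

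The plan's own 31 gives 31 × 0.8 = 24.8 completers, and 25/31 = 81% analysed. Only failures with an evaluable 0-6 h record are avoidable, so the saving lies between nil and the column of extras.

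**5. Day 1.** The primary model (SAP 11.1.5.2) uses one Day 1 quantity, the post-dialysis pre-challenge SBP. SAP 14.6.6 takes it from the first ABPM reading or, failing that, from the post-dialysis vital signs. A poor 24-hour recording on Day 1 therefore need not leave the model short of any term. The replacement wording in Protocol 9.2.1 and SAP 14.7.1 names AC2 only, while SAP 3.2 expects all 50 to have passed QC at both challenges.

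**The case against.** Much can be said for the plan.

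- **The criteria are unseen.** A reader might infer that usable 6-hour data *are* dropped because of poor wear later in the day. The documents do not support that. They say that the 24-hour results are checked, not that hours 6-24 alone can fail a recording, and a failed one may be poor throughout.
- **There is evidence the other way.** SAP 11.2.5.1 and 14.6.6 provide for more than 25% of subjects dropping out of the AUEC analysis for missing hour-24 readings, although the displays hold only QC-passing subjects. Some recordings are thus expected to pass with late readings missing. This weakens the inference. It does not show that long overnight gaps pass.
- **Power.** A reader might take 5-15% off 25 per arm and conclude that power falls to 85-89% (23.75 per arm gives 88.5%, 21.25 gives 84.7%). This does not follow, because 25 is the target after QC and AC2 failures are replaced.
- **Differential selection.** Nothing in the documents shows that QC failure differs by arm or tracks tolerance.
- **Safeguards exist.** The repeat AC2 may recover many failures. Table 4.37 restores failed recordings, SAP 14.6.6 requires its comparison with the primary result, and Table 4.42 reports QC passes by arm and day. SAP 11.1.3 also allows for exceptions to ITT.

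These points remove any claim of demonstrated loss or lost power. They leave the mismatch itself. The repeat is optional, and Table 4.37 mixes QC failures with imputed withdrawals, so it does not isolate the effect of the gate. Replacement restores numbers, but the excluded randomised subjects stay excluded.

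**Conclusion.** The concern holds in a limited form. By a stated rule, the primary analysis is a QC-passing subset under an ITT label, with the gate set on 24 hours and the endpoint on 6. That much rests on the text alone. Whether valid 0-6 h data are lost to later hours depends on the PRS: it is possible, not shown, and nil if the PRS judges 0-6 h separately. The exclusion for Day 1 failure is implied by SAP 11.1.4 and 14.6.6 rather than stated outright, and the primary model does not need it.

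Power stays near 90% as long as replacement reaches 25 analysable subjects per arm. At an assumed 5-15% final failure rate, the size is at most about 2-5 extra completers per arm, plus the exclusion of randomised subjects with an observed outcome. This is a cheap improvement worth making, not a flaw that undermines the primary comparison.

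**What to change.** In SAP 11.1.4 and 14.6.6, for the primary endpoint only:

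1. Replace the 24-hour QC gate at AC2 with a 0-6 h evaluability rule, with the minimum number of valid readings per hour set by the sponsor before database release. If the PRS already contains such a rule, quote it. SAP 14.6.6 shows how to average but sets no minimum, and one reading per hour would be a debatable choice.
2. Do not exclude a subject for Day 1 QC failure when a Day 1 pre-dose SBP exists.
3. State which recording counts when AC2 was repeated. SAP 14.6.6 now bars the original from any analysis once a repeat exists, and a 0-6 h rule could leave two eligible recordings.
4. Keep the 24-hour criterion for AUEC and the 24-hour averages.
5. Name the Table 4.5 set AC2-evaluable.

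The cost is mostly SAP wording, because 6-hour averages for failed recordings are already planned for Table 4.37. The downside is slightly noisier 6-hour averages for a few subjects. Renaming the set adds accuracy but little else, since the comparison with Table 4.37 is already required.

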9.2. Sample Size Considerations

9.2.1. Sample Size Assumptions

It is expected that 31 subjects will be randomized into each treatment arm. Assuming a 20% withdrawal rate during the Hgb Maintenance Period, there will be 25 subjects per treatment arm that will undertake Acute Challenge 2. The study will continue to recruit subjects until it is projected that 25 subjects per treatment arm complete and pass QC for Acute Challenge 2.

Assuming a 5% significance level and a true standard deviation (SD) of 16 mmHg for average SBP over 6 hours, a sample size of 25 subjects per treatment group will provide greater than 90% power to detect a -15 mmHg difference between treatment groups. Under these assumptions, statistical significance will be obtained if there is more than a 9.1 mmHg mean difference observed in favor of daprodustat.

Table 6 Power and Half-width of 95% CI for pair-wise comparisons, assuming a 16 mmHg SD for average SBP over 6 hours

Challenge	Expected Number of Subjects per Treatment Group	Power to detect 15 mm Hg difference	Half-Width of 95% CI ²
Acute Challenge 1	31	95%	8.1 mmHg
Acute Challenge 2 ¹	25	90%	9.1 mmHg

¹ Primary Comparison² Minimal detectable effect

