9.4. Key Elements of Analysis Plan

9.4.1. Primary Analyses

The primary analysis of average SBP over 6 hr post-dose during Acute Challenge 2 will be an analysis of covariance (ANCOVA) with terms for treatment, prior ESA dose (low/high), and post-HD/pre-Acute Challenge 1 SBP, difference between post-HD/pre-Acute Challenge 2 SBP and post-HD/pre-Acute Challenge 1 SBP, and treatment by (difference in post-HD SBP between Acute Challenge 1 and 2) interaction. Note that the pre-challenge SBP may change over time between Acute Challenge 1 and Acute Challenge 2 as a result of the maintenance therapy, and thus the pre-challenge SBP at Acute Challenge 2 is not a true pre-treatment covariate. As a result, the interpretation of the effect of the Acute Challenge 2 may be confounded by the impact of treatment phase on the covariate. Therefore, if the interaction term in this model is significant at the 0.10 level, then the primary model will be ANCOVA with terms for treatment, prior ESA dose (low/high), and post-HD/pre-Acute Challenge 1 SBP. The primary model will provide a point estimate and two-sided 95% CI for the treatment effect and a p-value for the superiority assessment. Superiority will be established if the p-value is <0.05.

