**CONFIDENTIAL**

205665

will be assessed by plotting the residuals against the predicted values for the model. If assumptions are grossly violated, alternative analyses will be considered.
Model Results Presentation

 
The point estimate, two-sided 95% CI and p-value for the difference between treatment groups will be presented from the selected final model for the superiority assessment. Superiority will be established if the p-value is <0.05.
 

Sensitivity and Supportive Analyses

 
If there are protocol deviations that are thought to potentially impact the primary endpoints (defined as at least 10% of the ITT population being excluded from the PP population), an exploratory sensitivity analysis will be completed. The analysis used for the primary endpoint will be repeated and similar results will be presented.
 
Participants who discontinue randomized study medication early will have their missing Day 57 AC2 ABPM data imputed; a sensitivity analysis will be run on the primary endpoint including these participants.
 
The primary endpoint will analyse using a 6-hour average of BP from ABPM device, sensitivity analyses using 8, 12, and 24-hour averages will be analysed using the primary model explained above in the model specification section.
 

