### 11.2.4. Strategy for Intercurrent (Post-Randomization) Events

If the primary sensitivity analysis for missing data differs with the primary endpoint, further sensitivity analyses on the secondary endpoints will be analysed. These potential, additional sensitivity analyses will follow how the primary endpoint sensitivity analysis was analysed, see Section 11.1.4 and Section 14.6.6 for details.

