
 
A sensitivity analysis will be performed on the primary endpoint to include those subjects who stop randomized treatment and those participants who fail any QC for their acute challenge. 
 
The first group are those participants who stop randomized treatment. These participants will have their Day 57 6hr average SBP ABPM data imputed to assess what would have happened had the participant not stopped IP. Since these participants would have been randomized, there will be data for acute challenge 1, however acute challenge 2 data will need to be imputed. 
 
Post-HD/pre-Acute Challenge 2 SBP will also be imputed.
 
 
 
The second group are those participants who have QC failed either their Day 1 or Day 57 acute challenge, or QC failed both acute challenges. For this group no data imputation will be performed, instead the data that is available from the ABPM device will be used to calculate what the 6hr average is. 
 
Like for the primary endpoint, post-HD/pre-Acute Challenge SBP will be taken from the first measurement on the ABPM device. If missing, then the vital signs BP will be used instead.
 
 
 
 
 
Multiple imputation for the first group, those participants who stop randomized treatment, will be done under the assumption of a multivariate normal distribution using the Markov Chain Monte Carlo (MCMC) procedure assuming missing at random. 
 
Both the pre AC2 SBP and Day 57 6hr average SBP will be imputed
 
The first step will be to calculate the number of missing data points to see what the missing pattern is
 
Next the imputation phase will fill in values for the missing data points 
 
Seed code of 205665 will be used
 
Burn in iterations and maximum iterations are set to default, 200
 
This will result in 1,000 imputations being calculated
 
Trace plots and autocorrelation figures will be used to assess the imputations
 
Variables to be included for imputation: 
 
Day 1 6 hr average SBP from ABPM
 
Day 1 baseline SBP
 
Day 57 baseline SBP
 
Day 57 6 hr average SBP from ABPM
 
Add treatment and prior esa dose as by variables in proc mi 
 
If there are error and or warning messages related to the by statement, try by randomized treatment only until no error/warning messages.
 
 
 
Next the imputed dataset will be used to calculate the difference between the pre AC1 and pre AC2 SBP, now using the imputed pre AC2 SBP.
 
 
 
 
 
 
 
	

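### The one missing-data sensitivity analysis for the primary endpoint mixes imputation for withdrawals with inclusion of QC-failed recordings, so its result cannot be attributed to either

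*SAP*

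**What the plan says.** SAP 14.6.6 limits the pharmacodynamic displays to participants whose ABPM passes QC. The primary analysis therefore leaves out two groups: those who stopped treatment and have no Acute Challenge 2 recording, and those whose recording failed QC.

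SAP 11.1.4 brings both back in a single analysis, covering participants who withdraw and "have their ABPM data imputed as well as those participants whose ABPM data did not pass QC for a given day". SAP 14.6.6 repeats this, including "those subjects who stop randomized treatment and those participants who fail any QC for their acute challenge". Only the first group is imputed (multivariate normal, MCMC, missing at random). The second group enters with whatever ABPM readings are available.

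The programming note for Table 4.37 (SAP 14.12.8) matches: "Use imputed missing values for AC2 for early withdrawal subjects, calculate 6hr averages for those subjects who failed QC for any AC".

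SAP 11.1.5.2 describes less: "Participants who discontinue randomized study medication early will have their missing Day 57 AC2 ABPM data imputed; a sensitivity analysis will be run". It does not mention QC failures.

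SAP 11.2.4 then gives the result a consequence. "If the primary sensitivity analysis for missing data differs with the primary endpoint", further sensitivity analyses of the secondary endpoints follow. SAP 14.6.6 contains the same trigger.

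**The concern.** A sensitivity analysis is informative when it changes one thing. This one changes both the handling of missing outcomes and the data-quality rule, and is then read as the missing-data check.

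If Table 4.37 differs from the primary result, the plan treats the difference as sensitivity to missing data, although the QC-failed recordings may be the cause. If it agrees, that may be robustness or two effects of opposite sign. The protocol expects 20% withdrawal, so robustness to dropout is the first thing a reader will want to know.

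**Working it through.** **1. The plan's own figures.** Protocol 9.2.1 gives the inputs: "Assuming a 5% significance level and a true standard deviation (SD) of 16 mmHg for average SBP over 6 hours", and "25 subjects per treatment group will provide greater than 90% power to detect a -15 mmHg difference". Section 9.4.1 specifies a "two-sided 95% CI for the treatment effect".

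- Half-width = t(0.975, 48 df) × SD × √(2/n) = 2.011 × 16 × √(2/25) = 9.10 mmHg.
- Power for 15 mmHg from the noncentral t distribution = 0.901.

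Both agree with protocol Table 6. The 9.1 mmHg half-width is the yardstick below.

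**2. Does any display separate the two changes?** The sensitivity tables for the primary endpoint in SAP 14.12.8 are:

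- 4.36: per-protocol population
- 4.37: the combined analysis
- 4.38 to 4.40: 8-, 12- and 24-hour averages

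Table 4.42 only counts QC passes. None isolates the imputation or the QC-failed data.

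**3. Who is in the combined analysis.** Protocol 9.2.1 expects 31 randomised per arm and 20% withdrawal: 31 × 0.8 = 24.8, so about 25 complete and 6 withdraw. SAP 14.7.1 replaces QC failures until 25 per arm pass. With m QC failures per arm, the combined analysis therefore holds 25 + 6 + m = 31 + m per arm. The documents do not give m.

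**4. Shift caused by the QC-failed recordings.** Let b be the differential bias (one arm minus the other) in their 6-hour averages. It is also not in the documents.

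- Imputation fitted to QC-pass data only: the bias sits in m of 31 + m values, so the shift is b·m/(31 + m).
- Imputation fitted to QC-pass and QC-failed data: imputed values on average inherit the shift of the fitted data, so the shift is b·m/(25 + m).

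| m per arm | b (mmHg) | Fitted to QC-pass only | Fitted to both |
|---|---|---|---|
| 1 | 5 | 5/32 = 0.16 | 5/26 = 0.19 |
| 3 | 10 | 30/34 = 0.88 | 30/28 = 1.07 |
| 3 | 15 | 45/34 = 1.32 | 45/28 = 1.61 |
| 6 | 15 | 90/37 = 2.43 | 90/31 = 2.90 |

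Over m = 1 to 6 and b = 5 to 15, the two fitting choices differ by at most 2.90 − 2.43 = 0.47 mmHg. The mixing arises under either.

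**5. Can the combined result be attributed?** This was simulated with 1,500 trials per setting. Assumptions: 25 QC-pass, 6 withdrawn and 3 QC-failed per arm; correlation 0.6; bias in the epoetin arm only; multivariate normal imputation within arm; ANCOVA on treatment and SBP before Acute Challenge 1. Run (a) adds imputed withdrawals to QC-pass data. Run (b) adds QC-failed data without imputation. Entries are mean shifts from the primary estimate (daprodustat minus epoetin, mmHg).

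| Setting | (a) | (b) | Combined, fitted to QC-pass | Combined, fitted to both |
|---|---|---|---|---|
| Random dropout, no bias | 0.03 | −0.03 | 0.01 | 0.01 |
| Missing-at-random dropout, no bias | −1.19 | 0.05 | −1.05 | −1.04 |
| Random dropout, bias +15 | 0.00 | −1.62 | −1.33 | −1.63 |
| Missing-at-random dropout, bias −15 | −1.24 | 1.65 | 0.23 | 0.51 |

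In the combined columns, the second and third settings look alike and the fourth looks close to robust. Runs (a) and (b) tell them apart on average.

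In the no-bias setting, the SD of the shift across simulated trials was 0.89 for (a), 1.22 for (b) and 1.33 to 1.50 for the combined run. A 1 mmHg movement in a single trial can therefore be chance. Separate runs show which change moved the estimate, not that the movement is systematic.

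**The case against.** The strongest reply is that the effect is probably small and its consequence limited. Much of that stands.

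- SAP 14.6.6 flags poor-quality readings and leaves them out of the averages, so a QC-failed recording contributes only its remaining readings. QC covers the full 24 hours under a specification outside these documents, so a recording might fail for reasons unrelated to the first six hours.
- Nothing in the documents supports a one-arm bias of 5 to 15 mmHg, and equal bias in both arms would cancel.
- The QC-failed group includes participants who failed only on Day 1 and may have a sound Day 57 outcome. The repeat Acute Challenge 2 should also reduce Day 57 failures.
- The superiority decision does not use Table 4.37. The trigger only adds secondary sensitivity analyses, and SAP 5.5 treats secondary testing as exploratory.
- The simulation simplifies the plan. It does not impute by prior ESA dose, and it uses the SAP's reduced ANCOVA rather than the model with the difference and interaction terms.

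These points limit the size. They do not separate the two changes.

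Some stronger readings are tempting but not supported:

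- *The imputation is contaminated by failed recordings.* SAP 14.6.6 says who is imputed and with which variables, but not which data fit the model. The question is open.
- *Section 11.1.5.2 contradicts 11.1.4.* It omits the QC-failed group; it does not exclude it.
- *The trial has no other missing-data sensitivity analysis.* A conditional hour-23 carry-forward exists for the Acute Challenge 2 SBP AUEC (Table 4.41). The point holds for the primary endpoint only.
- *The trial could never show robustness to dropout.* The collected data would allow a separate run; it is just not prespecified.

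**Conclusion.** The point holds for the primary endpoint. Its only missing-data sensitivity analysis combines two unrelated changes, no display separates them, and the combined result is acted on as a missing-data check. A difference cannot be attributed, and agreement is not clear evidence of robustness. This follows from the text and needs no assumption about size.

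The size is illustrative: about 0.2 to 2.9 mmHg for 1 to 6 QC failures per arm and a differential bias of 5 to 15 mmHg, given 25 QC-pass and 6 withdrawn per arm. That is modest against 9.1 mmHg. The primary analysis is unaffected. The case for change is that a prespecified, interpretable answer on dropout costs very little.

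**What to change.** Report separately:

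- (a) QC-pass data plus multiple imputation for early withdrawals, with the imputation model fitted to QC-pass data and this stated in 14.6.6;
- (b) QC-pass data plus the available QC-failed data, without imputation;
- (c) the combined run, if still wanted.

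Base the trigger in 11.2.4 and 14.6.6 on (a). Align 11.1.5.2 with this list, and add an exception for these tables to the QC-pass-only rule in 14.6.6. Also state what happens when a participant who withdraws has a QC-failed Day 1 recording, because the Day 1 average is an imputation variable.

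The cost is two extra runs of planned code and two tables.
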